9.2.2. Analysis of Key Secondary Endpoints

The key secondary endpoints will be evaluated using a mixed model repeated measures ANCOVA with an unstructured covariance matrix (or as appropriate); center and subject-within-center as random effects; treatment, visit, TTR genotype (variant and wild-type), and visit-by-treatment interaction, as fixed effects and Baseline score as covariate.

The key secondary variables are:

1. Change from Baseline to Month 30 in distance walked during the 6MWT ([Appendix 4](#)).
2. Change from Baseline to Month 30 in KCCQ ([Appendix 1.1](#)) Overall Summary score.

To maintain the type 1 error rate at or below the specified level, a pre-specified hierarchical order for testing as indicated above will be used to maintain the overall alpha at 0.05 for these two key secondary endpoints. The multiplicity procedure will be applied to the ITT analysis set only.

Supplemental analyses of the two key secondary variables will be performed to support the robustness of the conclusions drawn. The pattern-mixture analysis will group the subjects on the basis of their dropout or missing-data patterns. A grouping variable for this analysis is defined in the SAP.

Exploratory analyses of the key secondary endpoints will include results from the MMRM analysis at each individual time point other than Month 30.

Additional exploratory analyses of the key secondary endpoints will include results from the MMRM analysis at each individual time point by dose group (randomized dose group), TTR genotype (variant and wild-type), and NYHA Baseline classification. Descriptive statistics overall, by dose, by TTR genotype, and by NYHA Baseline classification will be provided for each time point.

Except for the analyses by dose, all analyses of the key secondary endpoints, including the proposed exploratory analyses of these endpoints, will compare the pooled tafamidis group with the placebo group.

9.3. Analysis of Secondary Endpoints

As a secondary analysis, the components of the primary endpoint (ie, all-cause mortality and frequency of cardiovascular-related hospitalizations) will be analyzed separately. All-cause mortality will be analyzed using SAS Proc Lifetest; p-values will be from the log-rank test. Kaplan-Meier survival curves for each treatment group along with median survival times (if applicable) will be presented.

All-cause mortality will also be analyzed using Cox proportional hazards model with treatment, TTR genotype (variant and wild-type), and NYHA Baseline classification (NYHA Classes I and II combined and NYHA Class III) as factors. Frequency of cardiovascular-related hospitalizations will be analyzed using a Poisson regression analysis with treatment, TTR genotype (variant and wild-type), NYHA Baseline classification (NYHA Classes I and II combined and NYHA Class III), treatment-by-TTR genotype interaction, and treatment-by- NYHA Baseline classification interaction terms as factors adjusted for treatment duration.

Cardiovascular-related mortality will also be analyzed using the Kaplan-Meier and Cox proportional methods described above.

All the analyses on the secondary endpoints described above will additionally be presented by TTR genotype (variant versus wild-type), NYHA Baseline classification, as well as dose (randomized dose group), and will be considered exploratory.

The proportion of subjects who achieved TTR stabilization in each treatment group at Month 1 will be compared using a Cochran-Mantel-Haenszel (CMH) test for proportions stratified by TTR genotype and Baseline severity (NYHA Classes I and II combined and NYHA Class III). The analysis will be performed separately by TTR genotypes (variant and wild-type) using a CMH test for proportions stratified by Baseline severity (NYHA Classes I and II

combined and NYHA Class III). The analysis will also be performed separately by Baseline severity (NYHA Classes I and II combined and NYHA Class III) using a CMH test for proportions stratified by TTR genotypes (variant and wild-type).

Analyses of TTR stabilization at Month 1 by dose (low vs. placebo and high vs. placebo) will be compared using a Cochran-Mantel-Haenszel (CMH) test for proportions stratified by TTR genotype and Baseline severity (NYHA Classes I and II combined and NYHA Class III).

A similar test of proportion will be done on TTR stabilization at all other time points and considered exploratory. No subgroup analyses will be done at these other time points.

Except for the analyses by dose group, all analyses of the secondary endpoints, including the proposed exploratory analyses of these endpoints, will compare the pooled tafamidis group with the placebo group.

9.4. Analysis of Exploratory Endpoints

The primary analysis will be repeated by the dose group to which subjects were randomized (tafamidis 20 mg vs. placebo and tafamidis 80 mg vs. placebo) to explore the effect by dose group.

Subgroup analysis using the Finkelstein-Schoenfeld method comparing the pooled tafamidis group and the placebo group, similar to that of the primary analysis, will also be done by the TTR genotype (variant type and the wild-type) and Baseline severity (NYHA Classes I and II combined and NYHA Class III) status.

Frequency of all-cause hospitalization will be analyzed using a Poisson regression analysis with treatment, TTR genotype (variant and wild-type), NYHA Baseline classification, treatment-by-TTR genotype interaction, and treatment-by-NYHA Baseline classification interaction terms as factors adjusted for treatment duration.

Cardiovascular-related days hospitalized and all-cause days hospitalized will be analyzed using an analysis of variance (ANOVA) with treatment, TTR genotype (variant and wild-type), NYHA Baseline classification (NYHA Classes I and II combined and NYHA Class III), treatment-by-TTR genotype interaction, and treatment-by- NYHA Baseline classification interaction terms as factors.

An exploratory analysis based on the Finkelstein-Schoenfeld method similar to that of the primary analysis will be done for each of the combinations of variables listed below:

1. All-cause mortality and frequency of all-cause hospitalization.
2. All-cause mortality and cardiovascular-related days hospitalized.
3. Cardiovascular-related mortality and frequency of cardiovascular-related hospitalization.

The exploratory endpoints listed below will be evaluated at each time point post-Baseline using a MMRM with an unstructured covariance matrix (or as appropriate) with center and subject-within-center as random effects and treatment, visit, TTR genotype (variant and wild-type), and visit-by-treatment interaction, as fixed effects and Baseline score as covariate where applicable (for example, no Baseline will be used as a covariate for PGA):

1. Change from Baseline in Kansas City Cardiomyopathy Questionnaire: (KCCQ) ([Appendix 1.1](#)) domain scores (Physical limitation, Symptom stability, Symptom frequency, Symptom burden, Self-efficacy, Social limitation, and Quality of life) and domain summary scores (Functional summary and Clinical summary).
2. Change from Baseline in EuroQoL-5 Dimensions (EQ-5D-3L) ([Appendix 2](#)) Index Score and visual analog scale (VAS) scores.
3. Patient Global Assessment ([Appendix 3](#)).
4. Change from Baseline in modified Body Mass Index.
5. Change from Baseline in NT-proBNP concentration.
6. TTR concentration and oligomer concentration.
7. Change from Baseline in select echocardiographic parameters:
 - a. End-diastolic interventricular septal wall thickness (mm);
 - b. Left ventricle posterior wall thickness (mm);
 - c. Left ventricular ejection fraction (%);
 - d. Left ventricular stroke volume (mL).
 - e. Global longitudinal strain;
 - f. Circumferential strain mid global;
 - g. Radial strain mid global.

All other echocardiographic parameters listed in [Section 7.6.5](#) will be analyzed descriptively.

An increase or decrease in NYHA classification relative to Baseline will be summarized using a shift table at each time point post-Baseline.

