7.7.1.3. Patient Global Assessment (PGA)

The subject's overall health status will be assessed by the PGA. At Baseline, subjects will be asked to rate their current health on the PGA using seven response options that range from "Normal, not at all ill" to "Among the most extremely ill". At follow-up visits subjects will be asked to rate the change in their health status since Baseline.

Subjects will complete the PGA at the Baseline visit and at Months 6, 12, 18, 24, and 30 (or Early Study Discontinuation) as listed in the [Schedule of Activities](#). Subjects should complete the PGA after the KCCQ ([Appendix 1.1](#)) and EQ-5D-3L ([Appendix 2](#)).

The PGA can be found in [Section Appendix 3](#).

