Appendix 3. PGA

PGA Item for Baseline Visit:

Taking your cardiomyopathy into account, would you say the state of your health is:

- Normal, not at all ill;
- Borderline ill;
- Mildly ill;
- Moderately ill;
- Markedly ill;
- Severely ill;
- Among the most extremely ill.

PGA Item for Follow-Up Visits:

Place an X in the box you feel most closely describes any change which you have experienced since beginning the study medication.

Take into account all change, whether or not you believe it is entirely due to drug treatment.

Choose only ONE response.

Since starting the study medication, my cardiomyopathy (HEART FAILURE) is:

- Very Much Improved
- Much Improved
- Minimally Improved
- No Change
- Minimally Worse
- Much Worse
- Very Much Worse

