6.4. Covariates

Baseline values will be included as a covariate in the analysis using the mixed model repeated measures (MMRM) model detailed in [Section 8.1.3](#). Where baseline scores are not available (or applicable) for the endpoints (eg, frequency of cardiovascular-related hospitalization), the NYHA baseline classification (NYHA Classes I and II combined and NYHA Class III) will be included in the appropriate models to address baseline severity levels.

All subjects who were incorrectly classified during randomization (wrong TTR Genotype or NYHA baseline classification) will be analyzed using the correct TTR Genotype or NYHA baseline classification values.

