8.1.3. Mixed Model Repeated Measures (MMRM) Analyses

The endpoints evaluated at multiple time points will be analyzed *using a mixed model repeated measures ANCOVA (MMRM) with an unstructured covariance matrix (or as appropriate); center and subject-within-center as random effects; treatment, visit, TTR genotype (variant and wildtype), and visit-by-treatment interaction, as fixed effects and Baseline score as covariate.* While the NYHA baseline classification may serve as an indicator of baseline severity, the endpoints that are evaluated at baseline (and at multiple points post-baseline) will use their respective baseline scores as the appropriate covariate for the MMRM analysis described above.

For the analyses by TTR genotype, the same model specified above will be used, with the addition of terms for TTR genotype-by-treatment interaction and TTR genotype-by-treatment-by-visit 3-way interaction. Similarly for dose, the same model specified above will be used with replacement of “dose” for “treatment”. Appropriate CONTRAST statements will be used to generate the LSMEANS from the MMRM model (eg, for dose, 20 mg vs placebo and 80 mg vs placebo) at each post-baseline study visit. The subgroup analysis by NYHA baseline classification (NYHA Classes I and II combined and NYHA Class III) will be done using ANCOVA (MMRM) with an unstructured covariance matrix (or as appropriate); center and subject-within-center as random effects; treatment, visit, TTR genotype (variant and wildtype), NYHA baseline classification, visit-by-treatment interaction, NYHA baseline classification-by-treatment interaction, NYHA baseline classification-by-treatment-by-visit 3-way interaction as fixed effects and baseline score as covariate. All the subgroup analyses will be considered exploratory.

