- All-cause mortality and frequency of all-cause hospitalizations,
- All-cause mortality and cardiovascular-related days hospitalized using the Finkelstein-Schoenfeld analysis,
- Cardiovascular-related mortality and frequency of cardiovascular-related hospitalization using the Finkelstein-Schoenfeld analysis.

The exploratory endpoints listed below will be evaluated at each time point post-baseline using a mixed model repeated measures ANCOVA (MMRM) as detailed in [Section 8.1.3](#).

- Change from Baseline in Kansas City Cardiomyopathy Questionnaire: (KCCQ) domain scores (Physical limitation, Symptom stability, Symptom frequency, Symptom burden, Total symptom, Self-efficacy, Social limitation, and Quality of life) and clinical summary score,
- Change from Baseline in EuroQoL-5 Dimensions (EQ-5D-3L) Index Score and visual analog scale (VAS) scores,
- Patient Global Assessment,
- Change from Baseline in Modified Body Mass Index,

- Change from Baseline in NT-proBNP concentration,
- TTR oligomer concentration at each time point,
- TTR concentration at each time point,
- Change from Baseline in echocardiographic parameters:
 - End-diastolic interventricular septal wall thickness (mm),
 - Left ventricle posterior wall thickness (mm),
 - Left ventricular ejection fraction (%),
 - Left ventricular stroke volume (mL),
 - Global longitudinal strain,
 - Circumferential strain mid global,
 - Radial strain mid global.

All other echocardiographic parameters listed as endpoints in [Section 6.1.4](#) will be analyzed descriptively.

The TTR oligomer concentration and TTR concentration will additionally be analyzed by dose. Descriptive statistics are presented by visit for the NYHA Classification (Class I, II, III, and IV). The number and percent of subjects with an improvement (decrease by at least one classification), those who worsened (increase by at least one classification), and those with no change (same classification) from baseline are presented at each visit using a shift table. A cross-tabulation of baseline severity level and post baseline change level will be presented at each visit for Patient Global Assessment scale.

Plasma concentrations of tafamidis will be summarized with descriptive statistics (n, arithmetic mean, standard deviation, coefficient of variation, geometric mean, median, and minimum and maximum) by dose, visit, and nominal time.

Plasma concentrations of diflunisal will be provided as listings by visit.

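### Protocol 9.4 bars a baseline covariate from the Patient Global Assessment model, the SAP does not carry that exception over, and the two should be reconciled by naming one covariate

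*Protocol*

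**What the plan says.** Protocol 9.4 lists PGA among the exploratory endpoints analysed by the repeated-measures model. The baseline score enters where applicable, and PGA is the named example of where it does not: "no Baseline will be used as a covariate for PGA". The fixed effects listed there include TTR genotype but not NYHA class.

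The PGA is nevertheless completed at Baseline and at Months 6, 12, 18, 24 and 30 (Protocol 7.7.1.3). The two items differ:

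- **Baseline:** "At Baseline, subjects will be asked to rate their current health on the PGA using seven response options". The item in Protocol Appendix 3 begins "Taking your cardiomyopathy into account, would you say the state of your health is" and grades severity.
- **Follow-up:** "At follow-up visits subjects will be asked to rate the change in their health status since Baseline". The item in Appendix 3 begins "Since starting the study medication, my cardiomyopathy (HEART FAILURE) is" and grades improvement or worsening.

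SAP 8.2.4 lists PGA among the endpoints analysed as in SAP 8.1.3 and does not repeat the protocol's exception. SAP 8.1.3 has the baseline score as covariate and says that "the endpoints that are evaluated at baseline (and at multiple points post-baseline) will use their respective baseline scores". SAP 6.4 gives a fallback: "Where baseline scores are not available (or applicable) for the endpoints", NYHA baseline class (I and II combined versus III) goes into the appropriate models. The only use of the baseline PGA item that the SAP states outright is descriptive: "A cross-tabulation of baseline severity level and post baseline change level will be presented at each visit for Patient Global Assessment scale" (SAP 8.2.4).

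**The concern.** Three sections bear on one model, and they lead to three answers: no severity covariate (Protocol 9.4), the baseline PGA rating (SAP 8.1.3 read literally), or NYHA class (SAP 6.4, if the baseline rating is held not applicable). A programmer could defend any of them, and the choice could be made after results are seen.

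The protocol's answer also leaves unused a measurement that the trial already takes. A covariate need not share the outcome's scale. Baseline severity may well be related to the later change rating: a subject who starts in the healthiest category has little room to report improvement. If the two are related, leaving baseline severity out widens the interval for the pooled tafamidis versus placebo contrast and leaves it open to chance imbalance in initial severity. The planned cross-tabulation does not adjust that contrast.

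**Working it through.** **1. The passages side by side**

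| Source | Covariate for the PGA model |
|---|---|
| Protocol 9.4 | No baseline score; no NYHA term in the model |
| SAP 8.2.4 | Refers PGA to 8.1.3; exception not repeated |
| SAP 8.1.3, literal reading | Baseline PGA rating |
| SAP 6.4, if that rating is not applicable | NYHA baseline class |
| SAP 8.1.3 main model and Appendix 1.3 code | Baseline score, treatment, visit, genotype, treatment-by-visit, with center as a random effect; no NYHA term |

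The 8.1.3 model for subgroups by NYHA class does contain NYHA, but SAP Table 2 marks PGA for the overall analysis only, so that model is not applied to it. Protocol section 9 allows the SAP to modify protocol analyses, but the SAP does not say that it does so for PGA. The only PGA change in the SAP's amendment history is the added cross-tabulation.

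**2. Possible effect on precision**

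The documents give no power, effect size, SD or correlation for PGA, so there is no planned figure to reproduce. The inputs are:

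- 160 placebo and 160 + 80 = 240 pooled tafamidis subjects (Protocol 3).
- Two-sided alpha of 0.05 (SAP 4.2).
- *Assumed:* 80% power without the covariate, as a reference point only.
- *Assumed:* r, the within-arm correlation of baseline severity with the follow-up rating, from 0 to 0.6. Its sign does not matter.

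The standardised effect giving 80% power unadjusted is

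d = (1.960 + 0.842) × √(1/160 + 1/240) = 2.802 × 0.1021 = 0.286 SD.

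With the covariate, residual variance is multiplied by 1 − r², so

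power = Φ(2.802/√(1 − r²) − 1.960).

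For r = 0.3: 2.802/√0.91 = 2.937, and Φ(0.977) = 83.6%.

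| r | Variance reduction | Power |
|---|---|---|
| 0 | 0% | 80.0% |
| 0.1 | 1% | 80.4% |
| 0.2 | 4% | 81.6% |
| 0.3 | 9% | 83.6% |
| 0.4 | 16% | 86.4% |
| 0.5 | 25% | 89.9% |
| 0.6 | 36% | 93.8% |

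A rough guide to r: suppose the change rating behaved like a true difference between two states of equal variance with correlation ρ between them. Then |r| = √((1 − ρ)/2). For assumed ρ from 0.5 to 0.9, |r| runs from 0.50 to 0.22 and the variance reduction from 25% to 5%. A global impression of change need not behave this way, so this does not establish r.

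**3. Validity**

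A single-visit simulation with seven-level ratings, 160 versus 240 subjects and 4,000 runs per setting gave type I error of 5.1% to 5.3% with or without the covariate. Power without and with it, at the same d before rounding to seven levels, was:

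- r = 0: 77.7% and 77.6%
- r = 0.3: 78.4% and 81.6%
- r = 0.5: 77.9% and 87.4%

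Leaving the covariate out does not distort the test, and including it costs essentially nothing when it is uninformative.

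**The case against.** The strongest reply is that the exception was deliberate. The analysed variable is a change rating, so it has no baseline value of its own, and Protocol 9.4 names PGA for that reason. On that view 8.1.3 does not reach PGA, because a change rating is not evaluated at baseline. SAP 6.4 does foresee baseline scores that are not applicable, with hospitalization frequency as its example, and NYHA class does appear in the Cox, Poisson and ANOVA models. This much stands: a reader might infer that the sponsor overlooked the baseline item, and the documents do not support that. The reply still leaves the 6.4 fallback with no term in the main 8.1.3 model, and a different response scale explains the omission without being a reason against the covariate.

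A second reply is that if the SAP governs and 8.1.3 is read literally, baseline PGA is already in the model. That is a fair reading, but it is one of three, and the SAP does not choose.

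Four other stronger readings should be set aside:

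- **That the missing-at-random assumption fails.** The model conditions on each subject's earlier PGA ratings, on genotype and on center. Early-discontinuation ratings are collected and mapped to visits (SAP Appendix 1.2). Baseline severity might help, but its absence does not undo the assumption.
- **That PGA is alone in lacking severity adjustment.** TTR concentration and oligomer concentration are in the same list, and their own baselines are assay levels rather than severity measures.
- **That precision is certainly lost.** That depends on r, which the documents do not give.
- **That both baseline PGA and NYHA class must be included.** SAP 6.4 and 8.1.3 make NYHA class the substitute for a baseline score, so requiring both goes beyond the SAP's own rule.

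**Conclusion.** The point holds as a minor specification conflict with an inexpensive improvement attached. Protocol 9.4 and SAP 6.4, 8.1.3 and 8.2.4 do not together determine the covariate in the PGA model. The protocol's version is valid, with no type I error inflation in the check, but it may be less precise than it could be.

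The variance reduction forgone is 0% at r = 0, 9% at r = 0.3 and 25% at r = 0.5. From an assumed 80% power these correspond to 80.0%, 83.6% and 89.9%. They are single-visit figures that rest on an assumed r and an assumed reference power. The 8.1.3 model fits one baseline slope across visits and already contains genotype and center, so the actual gain would depend on the correlation left after those terms and could vary by visit.

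PGA is exploratory and outside the alpha-controlled hierarchy (SAP 8.2.2), so nothing here touches the primary or key secondary conclusions.

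**What to change.** 1. In Protocol 9.4, delete the parenthesis that exempts PGA.
2. In SAP 8.1.3 or 8.2.4, state that the PGA model uses the Baseline PGA severity rating as its baseline covariate, and say whether it enters as categories or as an ordinal score. Settle this before unblinding.
3. If the sponsor judges that item not applicable, say so with the reason, use NYHA baseline class (I and II combined versus III) as SAP 6.4 directs, and add that term to the 8.1.3 model for PGA.

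One of the two covariates is enough. The cost is one or two sentences in the SAP and one deletion in the protocol, with no new data. An ordinal score or the two-level NYHA class uses one degree of freedom; seven categories use 7 − 1 = 6. Because Protocol section 9 lets the SAP modify protocol analyses, the SAP sentence can settle the analysis, and the protocol edit removes the contradiction.

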9.4.1. Pharmacokinetic Data

Plasma concentrations of tafamidis will be summarized graphically and with descriptive statistics (n, arithmetic mean, standard deviation, coefficient of variation, geometric mean, median, and minimum and maximum) by visit and nominal time. Due to the sparse nature of the pharmacokinetic sampling scheme, a population approach will be used for pharmacokinetic data analysis. Nonlinear mixed-effect modeling will be performed to characterize the pharmacokinetics of tafamidis. These tafamidis concentration data may be pooled with data from previous clinical studies for analysis. Results from any tafamidis concentration modeling conducted will be reportedly separately. If appropriate, these pharmacokinetic data may be used for exposure-response analyses.

To confirm adequate exposures following administration of soft gel capsules in the 80 mg dose group, the Month 1 PK samples from the first 50 subjects enrolled in the study will be analyzed and summarized by treatment to evaluate approximately 20 subjects assigned to the 80 mg dose. The PK sample collection time at the Month 1 visit targets the time of maximum tafamidis concentration at approximately 3 hours post-dose. The expected mean steady state tafamidis concentration is 8.0 ug/mL. If the geometric mean concentration from the 80 mg dose group is < 50% of the projected value, the 80 mg dose may be adjusted. The PK analyst reviewing de-identified tafamidis exposure data will be separate from study team members and will not have access to any unblinded safety or efficacy data. Details of the analysis procedure will be documented in a PK unblinding plan.

